## **11. Modification from the Planned Statistical Analysis in Protocol**

### **11.1. Interim Analysis**

Interim analyses may occur at any time during the OLE as determined by Fulcrum. In general, the unblinded [REDACTED] Biostatistics and Programming team will use unblinded data to program tables, listings and figures (TLFs) based on the SAP.

### **11.2. Open-label Analysis Set**

The protocol defines the Open-label analysis set for subjects who complete 24 weeks of treatment in the placebo-controlled treatment period and receive at least 1 dose of open-label losmapimod in the OLE.

This analysis set will also include subjects who complete 48 weeks of treatment in the placebo-controlled treatment period and receive at least 1 dose of open-label losmapimod in the OLE.

## **12. Safety Review Committee (SRC)**

The SRC will continue to meet and review the data from the OLE. These meetings will be planned at regular intervals. Details about data to be presented will be provided in the SRC Charter. The SRC may convene ad hoc meetings based on rates of SAEs if safety concerns arise during the trial. After its assessment, the SRC will recommend continuation, modification or termination of the clinical trial.

The [REDACTED] Biostatistics and Programming will prepare the safety tables, listings and/or figures using the actual randomization and materials/kits schedule.

## **14. Appendices**

## 14.1. Derivation of MRI Composite Scores

### Input to the Statistical Plan for FSHD analysis

#### Muscle categorization

Each muscle is categorized into one of three categories:

- A. 'Normal' muscles are normal appearing (low MFI and MFF, muscle likely unaffected by disease)
- B. 'Affected' muscles have a likely disease involvement (intermediate MFI and MFF)
- C. 'End-stage' corresponds to that more than 50% of the muscle tissue has been replaced by fat, and most of the functional capacity is likely lost

Muscle category	MFF criteria	MFI criteria
A. Normal	MFF < 50%	AND
B. Affected	MFF < 50%	AND
C. End-stage	MFF ≥ 50%	-

#### Quality control of measurements

Trained anatomical imaging experts evaluate the signal quality in each muscle. If a muscle is not analyzable, that muscle is marked as not analyzable and no measurements will be extracted from it. For cross-sectional analysis minor quality issues are accepted, but not for longitudinal analysis. Hence, as seen below, we'll use different statistical inclusion parameters depending on if we are doing a cross-sectional or longitudinal analysis.

#### Statistical inclusion parameters

The muscle categorization and quality control results are summarized in 3 statistical inclusion parameters which will be provided for each muscle:

- Statistical Inclusion Category: Can take the values **A**, **B** or **C**, which correspond to 'Normal', 'Affected' and 'End-stage'. Abbreviated **SIcat** in equations.
- Statistical Inclusion Cross-sectional: Can take the values **0** or **1** (0 if there are major signal quality issues indicating unreliable measurement, 1 otherwise). Abbreviated **SIcross** in equations.
- Statistical Inclusion Longitudinal: Can take the values **0** or **1** (0 if there are any signal quality issues, including minor, 1 otherwise). Abbreviated **SIlong** in equations.

Note: In general, if a SI parameter is 'Unable to Assess', 'NA' or '0', that muscle should be excluded from the corresponding data analysis. As for other muscle measurements, the SI parameters will have a corresponding 'Quality Issues' column – these columns may be ignored.

#### Whole-body combined measurements

##### Cross-sectional analysis

MRI-based measurements from multiple muscles is combined to obtain global measurements of disease affection for correlation to disease severity or functional test scores in cross-sectional data:

$$\begin{aligned} LMV_{\text{tot}} &= \sum_{i \in \text{muscles}} SI_{\text{cross},i} \cdot LMV_i \\ MFI_{\text{tot}} &= \frac{\sum_{i \in \text{muscles}} SI_{\text{cross},i} \cdot MFI_i \cdot LMV_i}{\sum_{i \in \text{muscles}} SI_{\text{cross},i} \cdot LMV_i} \\ MFF_{\text{tot}} &= 1 - \frac{\sum_{i \in \text{muscles}} SI_{\text{cross},i} \cdot LMV_i}{\sum_{i \in \text{muscles}} SI_{\text{cross},i} \cdot TMV_i} \end{aligned}$$

$MFF_{\text{tot}}$  is likely to correlate best with functional tests as it reflects global muscle-to-fat replacement, while interpretation of total LMV at only one timepoint requires reference data for normal total LMV that is not available at the moment. Note that muscles are included regardless of category (A, B

 Note that AMRA® Researcher is for research purposes only, and the names of these categories do not correspond to any form of diagnosis.

**14.2. Protocol Version 4.0 Schedule of Study Procedures: Open-Label Extension (Visits will Occur Quarterly Until Study Drug Approval or Study is Discontinued)**

Procedure	Week 60 Week 108 Week 156 Week 204	Week 72 Week 120 Week 168 Week 216	Week 84 Week 132 Week 180	Week 96 Week 144 Week 192	ET Visit a	Safety Follow-Up 7 Days After the Last Dose of Study Drug
Visit Window (days) b	±7	±7	±7	±7		±3
Weight, height, and BMI c		X				
Urine pregnancy test e	X	X	X	X	X	X
Vital signs f	X	X	X	X	X	X
Physical examination g						X
Standard 12-lead ECG h	X	X	X	X	X	X
Serum chemistry	X	X	X	X	X	X
Hematology	X	X	X	X	X	X
Urinalysis	X	X	X	X	X	X
MSK MRI i		X		X	X j	
PK sampling k	X	X	X	X	X	
RWS	X	X	X	X	X	X
TUG (classic and FSHD)	X	X	X	X	X	X
Manual dynamometry	X	X	X	X	X	X
MFM Domain 1	X	X	X	X	X	
FSHD-HI questionnaire	X	X	X	X	X	X
PGIC questionnaire	X	X	X	X	X	X
Clinic visit	X	X	X	X	X	X
Study drug dispensation m	X	X	X	X		

Procedure	Week 60 Week 108 Week 156 Week 204	Week 72 Week 120 Week 168 Week 216	Week 84 Week 132 Week 180	Week 96 Week 144 Week 192	ET Visit a	Safety Follow-Up 7 Days After the Last Dose of Study Drug
Study drug count	X	X	X	X	X	
Concomitant medications b	Continuous from signing the ICF through the safety follow-up visit					
Concomitant treatments and procedures	Continuous from signing the ICF through the safety follow-up visit					
Adverse event monitoring	Continuous from signing the ICF through the safety follow-up visit					

Abbreviations: BMI, body mass index; ECG, electrocardiogram; ET, early termination; FSHD, facioscapulohumeral muscular dystrophy; FSHD-HI, Facioscapulohumeral Muscular Dystrophy Health Index; ICF, informed consent form; MFM, Motor Function Measure; MRI, magnetic resonance imaging; MSK, musculoskeletal; OLE, open-label extension; PGIC, Patients' Global Impression of Change; PK, pharmacokinetic(s); RWS, Reachable Workspace; TUG, Timed Up and Go.

- a If a subject prematurely discontinues study treatment during the OLE, they will be encouraged to remain in the study and continue with all other aspects of the study. If a subject decides to prematurely discontinue study treatment during the OLE and not continue with all other aspects of the study, they will be considered to have withdrawn from the study. If a subject withdraws from the study during the OLE, they will be asked to complete the ET visit as soon as possible after the decision to terminate study participation and to complete the safety follow-up visit 7 ( $\pm 3$ ) days after their last dose of study drug. If the ET visit will be scheduled more than 7 days after the last dose of study drug, the safety follow-up and ET visits may be combined, with no duplication of assessments required.
- b Scheduled visits may be split over 2 days if required, with a maximum of 5 business days in between visits. Unscheduled visits may be performed if clinically indicated. Subjects can travel for MRI or muscle biopsy if needed, but the use of a study-approved MRI scanner should be consistent during the trial.
- c Weight and height will be measured and BMI will be calculated once a year (ie, Week 48, Week 96, Week 144, etc.). Weight and height will be measured with shoes off and preferably with the same balance.
- d [REDACTED]
- e Urine pregnancy tests will be performed for all female subjects of child-bearing potential before dispensation of study drug. If pregnancy is found, subjects must be terminated from the study effective immediately.
- f Vital signs (pulse rate, respiration rate, blood pressure, and temperature) will be collected after the subject has been seated or recumbent for at least 5 minutes and before any 12-lead ECG assessment or blood sampling is performed.
- g Physical examination at the safety follow-up visit includes an evaluation of body systems, including but not limited to the following: skin; head, eyes, ears, nose, and throat; respiratory system; cardiovascular system; abdomen (liver, spleen); lymph nodes; neurological system; and MSK system. Symptom-directed physical examinations can occur at any time during the study if triggered by adverse events or if deemed necessary by the investigator.
- h Twelve-lead ECGs will be performed after subjects have been recumbent for at least 5 minutes. Twelve-lead ECGs will be performed after the measurement of vital signs and before any procedures that may affect heart rate (eg, blood sampling).

- i Subjects will be screened for any contraindications to MRI as per clinic standard practice.
- j The MRI at the ET visit will not be repeated if an MRI was completed during the previous 12 weeks.
- k Blood samples for PK will be collected after dosing at each clinic visit, preferably  $\geq 1$  hour after dosing.
- l [REDACTED]
- m The appropriate amount of study drug supply (losmapimod) will be given to the subject at each applicable visit to allow for dosing until their next scheduled study visit plus additional tablets to cover the visit window or additional study drug will be provided to the subject via a courier, as applicable. Study drug (losmapimod) will be administered as 2 tablets taken twice daily and should be taken with food.
- n All medications taken within 28 days before screening through the safety follow-up visit will be recorded.

**14.3. Protocol Version 5.0 Schedule of Study Procedures: Schedule of Events: Open-Label Extension (Visits Will Occur Quarterly Until 90 Days After Commercial Drug Availability Post Regulatory Approval or Study is Discontinued)**

Procedure	Week 60	Week 72	Week 84	Week 96	ET Visit a	Safety Follow-Up 7 Days After the Last Dose of Study Drug
Visit Window (days) b	±7	±7	±7	±7		±3
Weight, height, and BMI c		X				
Urine pregnancy test e	X	X	X	X	X	X
Vital signs f	X	X	X	X	X	X
Physical examination g						X
Standard 12-lead ECG h	X	X	X	X	X	X
Serum chemistry	X	X	X	X	X	X
Hematology	X	X	X	X	X	X
Urinalysis	X	X	X	X	X	X
PK sampling i				X	X	
Clinic visit	X	X	X	X	X	X
Study drug dispensation j	X	X	X	X		
Study drug count	X	X	X	X	X	
Concomitant medications k	Continuous from signing the ICF through the safety follow-up visit					
Concomitant treatments and procedures	Continuous from signing the ICF through the safety follow-up visit					
Adverse event monitoring	Continuous from signing the ICF through the safety follow-up visit					

Abbreviations: BMI, body mass index; ECG, electrocardiogram; ET, early termination; ICF, informed consent form; MRI, magnetic resonance imaging; MSK, musculoskeletal; OLE, open-label extension; PK, pharmacokinetic(s).

- a If a subject prematurely discontinues study treatment during the OLE, they will be encouraged to remain in the study and continue with all other aspects of the study. If a subject decides to prematurely discontinue study treatment during the OLE and not continue with all other aspects of the study, they will be considered to have withdrawn from the study. If a subject withdraws from the study during the OLE, they will be asked to complete the ET visit as soon as possible after the decision to terminate study participation and to complete the safety follow-up visit 7 ( $\pm 3$ ) days after their last dose of study drug. If the ET visit will be scheduled more than 7 days after the last dose of study drug, the safety follow-up and ET visits may be combined, with no duplication of assessments required.
- b Scheduled visits may be split over 2 days if required, with a maximum of 5 business days in between visits. Unscheduled visits may be performed if clinically indicated. Subjects can travel for MRI or muscle biopsy if needed, but the use of a study-approved MRI scanner should be consistent during the trial.
- c Weight and height will be measured and BMI will be calculated once a year (ie, Week 72, Week 120, Week 168, Week 216, etc.). Weight and height will be measured with shoes off and preferably with the same balance.
- d [REDACTED]
- e Urine pregnancy tests will be performed for all female subjects of child-bearing potential before dispensation of study drug. If pregnancy is found, subjects must be terminated from the study effective immediately.
- f Vital signs (pulse rate, respiration rate, blood pressure, and temperature) will be collected after the subject has been seated or recumbent for at least 5 minutes and before any 12-lead ECG assessment or blood sampling is performed.
- g Physical examination at the safety follow-up visit includes an evaluation of body systems, including but not limited to the following: skin; head, eyes, ears, nose, and throat; respiratory system; cardiovascular system; abdomen (liver, spleen); lymph nodes; neurological system; and MSK system. Symptom-directed physical examinations can occur at any time during the study if triggered by adverse events or if deemed necessary by the investigator.
- h Twelve-lead ECGs will be performed after subjects have been recumbent for at least 5 minutes. Twelve-lead ECGs will be performed after the measurement of vital signs and before any procedures that may affect heart rate (eg, blood sampling).
- i Blood samples for PK will be collected after dosing at the Week 144 clinic visit only, preferably  $\geq 1$  hour after dosing.
- j The appropriate amount of study drug supply (losmapimod) will be given to the subject at each applicable visit to allow for dosing until their next scheduled study visit plus additional tablets to cover the visit window or additional study drug will be provided to the subject via a courier, as applicable. Study drug (losmapimod) will be taken twice daily and should be taken with food.
- k All medications taken within 28 days before screening through the safety follow-up visit will be recorded.

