**Table 8-2. Muscles Considered in the MRI Cross-sectional Scores**

Test	Muscles		
	Upper Extremity	Trunk	Lower Extremity
FHSD TUG	Supraspinatus Infraspinatus	Pectoralis Major Rhomboideus	Quadriceps Hamstrings

Test	Muscles		
	Upper Extremity	Trunk	Lower Extremity
	Subscapularis Teres Minor Deltoid Biceps Brachii Triceps Brachii	Latissimus Dorsi & Teres Major Trapezius Serratus Anterior Paraspinal (C3-Sacrum)	Adductors Tibialis Anterior Gastrocnemius Medialis
Classic TUG	N/A	N/A	Quadriceps Hamstrings Adductors Tibialis Anterior Gastrocnemius Medialis
RWS	Supraspinatus Infraspinatus Subscapularis Teres Minor Deltoid Biceps Brachii Triceps Brachii	Pectoralis Major Rhomboideus Latissimus Dorsi & Teres Major Serratus Anterior	N/A

Spearman correlation coefficients will be used to assess relationships between the cross-sectional composite scores and classical and FSHD TUG and RWS results by visit. The Spearman correlation coefficient and p-value will be calculated and presented in a table. This will also be graphically presented using scatterplots. Specifically, the following relationships will be assessed:

- All muscles vs. FSHD-TUG
- LE vs. Classical TUG
- Dominant upper extremity vs. Dominant RWS
- Non-Dominant upper extremity vs. Non-Dominant RWS

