14.2.3.2.1.11	Table 14.2.3.2.1.11 Change from Baseline in Longitudinal Composite Lean Muscle Volume (LMV) through Data-Cut Date (ddmmmyyyy) by Age (< 50 years old and >= 50 years old) Open-label Analysis Set	Open-label Analysis Set	R	8.1	Efficacy	
14.2.3.2.2	Table 14.2.3.2.2 Change from Baseline in Lean Muscle Volume (LMV) through Data-Cut Date (ddmmmyyyy) by Individual Muscles Open-label Analysis Set	Open-label Analysis Set	R	8.1	Efficacy	
14.2.3.2.3	Table 14.2.3.1.3 Correlation Between Lean Muscle Volume Cross-sectional Results and FSHD TUG, Classic TUG, and RWS Results through Data-Cut Date (ddmmmyyyy) by Visit Open-label Analysis Set	Open-label Analysis Set	R	8.1	Efficacy	
14.2.3.2.4.1	Table 14.2.3.2.4.1 Annualized Change in Longitudinal Composite Lean Muscle Volume (LMV) through RCT+OLE Data-Cut Date (ddmmmyyyy) Open-label Analysis Set	Open-label Analysis Set	R	8.1	Efficacy	
14.2.3.2.4.2	Table 14.2.3.2.4.2 Annualized Change in Longitudinal Composite Lean Muscle Volume (LMV) in RCT Period Open-label Analysis Set	Open-label Analysis Set	R	OLE	Efficacy	
14.2.3.2.4.3	Table 14.2.3.2.4.3 Annualized Change in Longitudinal Composite Lean Muscle Volume (LMV) in OLE Period through Data-Cut Date (ddmmmyyyy) Open-label Analysis Set	Open-label Analysis Set	R	OLE	Efficacy	
14.2.3.2.5.1	Table 14.2.3.2.5.1 Annualized Change in Lean Muscle Volume (LMV) by Individual Muscles through RCT+OLE Data-Cut Date (ddmmmyyyy) Open-label Analysis Set	Open-label Analysis Set	R	8.1	Efficacy	
14.2.3.2.5.2	Table 14.2.3.2.5.2 Annualized Change in Lean Muscle Volume (LMV) by Individual Muscles in RCT Period Open-label Analysis Set	Open-label Analysis Set	R	OLE	Efficacy	
14.2.3.2.5.3	Table 14.2.3.2.5.3 Annualized Change in Lean Muscle Volume (LMV) by Individual Muscles in OLE Period through Data-Cut Date (ddmmmyyyy) Open-label Analysis Set	Open-label Analysis Set	R	OLE	Efficacy	
14.2.3.3.1.1	Table 14.2.3.3.1.1 Change from Baseline in Longitudinal Composite Muscle Fat Infiltration (MFI) through Data-Cut Date (ddmmmyyyy) Open-label Analysis Set	Open-label Analysis Set	U	8.1	Efficacy	
14.2.3.3.1.4	Table 14.2.3.3.1.4 Change from Baseline in Longitudinal Composite Muscle Fat Infiltration (MFI) through Data-Cut Date (ddmmmyyyy) by Sex Open-label Analysis Set	Open-label Analysis Set	R	8.1	Efficacy	

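### Cross-sectional total LMV is an unscaled sum over readable muscles, so its planned correlations with TUG and RWS mix disease with body size and, to a lesser degree, image quality (minor; supportive OLE analysis)

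*SAP*

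**What the plan says.** SAP Appendix 14.1 (Cross-sectional analysis) defines three whole-body scores:

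- LMV_tot = Σ SI_cross,i × LMV_i
- MFI_tot = Σ SI_cross,i × MFI_i × LMV_i / Σ SI_cross,i × LMV_i
- MFF_tot = 1 − Σ SI_cross,i × LMV_i / Σ SI_cross,i × TMV_i

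The flag SI_cross is "0 if there are major signal quality issues indicating unreliable measurement, 1 otherwise" (Statistical inclusion parameters). The quality-control paragraph adds: "If a muscle is not analyzable, that muscle is marked as not analyzable and no measurements will be extracted from it". Where a flag is 0 or not assessable, the general instruction is "that muscle should be excluded from the corresponding data analysis". No rescaling, imputation, minimum number of muscles or body-size term is given for the cross-sectional score. The 25 cl and 50 cl thresholds in SAP 8.1 A apply to longitudinal relative change only.

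SAP 8.1 C states the use: "Spearman correlation coefficients will be used to assess relationships between the cross-sectional composite scores and classical and FSHD TUG and RWS results by visit", with p-values. The list of planned tables includes, as item 14.2.3.2.3, "Correlation Between Lean Muscle Volume Cross-sectional Results and FSHD TUG, Classic TUG, and RWS Results", and item 14.2.7.2 in the list of figures is the matching scatterplot.

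The same appendix paragraph says that MFF_tot "is likely to correlate best with functional tests as it reflects global muscle-to-fat replacement", and that "interpretation of total LMV at only one timepoint requires reference data for normal total LMV that is not available at the moment".

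**The concern.** In a sum, leaving a muscle out is the same as giving it zero volume. A subject whose quadriceps could not be read looks like a subject who has lost it. Raw litres of lean muscle also depend on sex and stature. RWS, by contrast, is scaled by arm length (Protocol 6.4.1) and analysed as relative surface area (SAP 8.2.1), so one side of that correlation is free of body size and the other is not.

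What is at stake is interpretation. A weak LMV-function coefficient could be read as poor clinical relevance of muscle volume when the construction of the score produced it. The set of readable muscles can also differ between visits, so a change in the coefficient from one visit to the next need not reflect biology.

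**Working it through.** The documents give no expected correlation, failure rate or muscle volumes for this analysis, so there is no plan figure to reproduce. The first two steps are algebra on the appendix formulas; the rest is illustrative.

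**1. A failed muscle.** Take ten equal muscles, each with total volume 1 and fat fraction 0.3, hence lean volume 0.7.

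- All readable: LMV_tot = 10 × 0.7 = 7.0; MFF_tot = 1 − 7.0/10 = 0.30.
- One fails: LMV_tot = 9 × 0.7 = 6.3, a 10% fall; MFF_tot = 1 − 6.3/9 = 0.30, unchanged.

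With the unequal shares assumed in step 3, one failure removes 2% to 22.5% of LMV_tot. With unequal muscles a failure also alters the muscle mix in MFF_tot and MFI_tot, but the muscle is never counted as zero.

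**2. Body size.** Multiply every volume by s. LMV_tot becomes s × LMV_tot. In MFF_tot and MFI_tot the factor cancels.

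**3. Illustrative size of the effect.** The simulation used N = 80 (enrolment in SAP 4.8, an upper bound for the OLE), 400 replicates per cell, and the five Classic TUG muscle groups of Table 8-2 on two sides. Assumptions that are not in the documents: TUG depends only on the subject's fat fraction plus noise; body size is log-normal; each muscle fails independently of disease; shares are 2% to 22.5% of lower-limb volume per muscle. Entries are mean Spearman coefficients with TUG.

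| Size log-SD | Failure per muscle | Raw LMV_tot | Rescaled for failures | Size-normalised | Both | MFF_tot |
|---|---|---|---|---|---|---|
| 0 | 0 | -0.68 | -0.68 | -0.68 | -0.68 | 0.69 |
| 0 | 10% | -0.59 | -0.68 | -0.59 | -0.68 | 0.69 |
| 0.15 | 0 | -0.58 | -0.58 | -0.68 | -0.68 | 0.69 |
| 0.25 | 0 | -0.48 | -0.48 | -0.68 | -0.68 | 0.69 |
| 0.25 | 10% | -0.45 | -0.48 | -0.59 | -0.67 | 0.69 |
| 0.35 | 20% | -0.35 | -0.39 | -0.51 | -0.67 | 0.68 |

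Size dominates: it alone moves -0.68 to -0.48. Adding 10% failures then moves the coefficient by only 0.03. Once size is removed, the failure effect is no longer masked: at size log-SD 0.25, the size-normalised score falls from -0.68 to -0.59 at 10% failure. A size correction alone is therefore not enough.

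A second simulation (70 subjects, male/female volume ratio 1.3 to 1.45, residual size SD 12% to 15%) agrees. From a true value near -0.68, the raw sum gave -0.38 to -0.45 with every muscle readable and -0.34 to -0.41 with 5% to 10% failing.

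**4. Adjusting for sex and height.** In a check of the partial Spearman correlation the coefficient recovered to about -0.58 to -0.64, against 0.68 in absolute value for MFF_tot. This fits the table: if adjustment cut the size log-SD from 0.25 to 0.15, the coefficient would move from -0.48 to -0.58.

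**5. Cost of requiring every muscle to be readable.** With independent failures the proportion of complete subjects is (1 − q)^k.

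- Ten lower-limb muscles: 0.95^10 = 60%, 0.90^10 = 35% (48 or 28 of 80).
- FSHD TUG set, 7 + 6 + 5 = 18 groups counted once: 0.95^18 = 40%, 0.90^18 = 15% (32 or 12 of 80).

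**The case against.** The analysis is supportive and descriptive, and no decision depends on these coefficients. The appendix states the LMV caveat openly and already prefers MFF_tot, whose own correlation table is planned. The failure effect of 0.03 to 0.04 is small beside sampling error: at n = 70 and a coefficient near -0.4, the standard deviation is roughly (1 − 0.4²)/√69 = 0.10. Only major signal problems set SI_cross to 0, and nothing in the documents supports failure rates of 5% to 10%. The simulations treat absolute volume as noise. The public text of the appendix also stops mid-sentence just after the formulas, so a further handling rule cannot be excluded. All of this stands, and it limits the severity. It does not remove the defect: the formulas are complete as printed, and 8.1 C and the table and figure lists carry LMV into the correlations without the caveat.

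Three stronger readings are tempting.

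- A reader might infer that the key LMV endpoint is compromised. Protocol 7.6.1 names LMV change from baseline at Week 48 in the placebo-controlled period, which has a separate SAP. In this SAP, longitudinal LMV uses a different inclusion flag, SI_long, and has the minimum-volume rule in 8.1 A.
- A reader might infer that the correlation must be too weak. That holds only if size and failure are unrelated to function. If, for example, badly affected muscles fail more often, counting them as zero could strengthen the correlation; a link between sex or height and function could push it either way.
- A reader might infer that a single LMV value has no meaning. The appendix says only that interpreting it needs reference data not yet available.

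**Conclusion.** The point holds, at minor severity. By the appendix formulas, cross-sectional LMV_tot counts a failed muscle as zero and scales with body size; MFF_tot and MFI_tot do not. Its planned unadjusted correlations with TUG and RWS sit badly with the appendix's own caveat. If size and failure are unrelated to function, the correlation is weakened, mainly by size and only slightly by failures while size is left uncorrected. The amount is unknown: -0.68 falling to between -0.35 and -0.58 is the range of the tabulated cells with size variation and rests wholly on assumed inputs. The OLE primary safety endpoint and the LMV change endpoint are untouched.

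**What to change.** 1. In Table 14.2.3.2.3, report beside the unadjusted coefficient the partial Spearman correlation of LMV_tot with TUG and RWS, adjusted for sex and screening height. Both are already collected.
2. Do not let a failed muscle count as zero. Divide LMV_tot by the expected share of the composite's volume held by the included muscles: Σ SI_cross,i × LMV_i / Σ SI_cross,i × p_i, where p_i is the average share of muscle i among subjects with every muscle of that composite readable. Report the number of muscles included at each visit. Show the complete-muscle analysis only as a sensitivity check, since it could drop many subjects.
3. State in SAP 8.1 C that structure-function conclusions are drawn from MFF_tot.

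The cost is SAP wording, some programming and an assumption about average muscle shares. The simulation used known shares, so its near-full recovery is a best case; if few subjects have every muscle readable, the shares will be imprecise. Sex and height will also leave some size variation in the score.
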